### 8.0 SUBJECT EVALUATION

#### 8.1 On-Study Clinical Evaluations

Week	Visit Purpose	Procedures/Evaluations
0	Enrollment	Registration, Collection of Baseline Demographic and Clinical Data, Performance Status, Details regarding the patient's pathology.
--	Randomization	Patient will be randomized to either Arm A (Acupuncture) or Arm B (Waitlist Control)
1 +/-7	BCG Treatment 1	Patient will receive BCG instillation #1 with/without acupuncture intervention prior as per their study arm assignment Review of Medication List Urinanalysis Vital signs to include BP, pulse, temperature

		
Assessment of ability to retain intravesical instillation for the desired dwell time (1-2 hours). Anticholinergic medications may be prescribed per clinic protocol if the patient complains of bladder spasms
 
Brief physical exam: perineal and abdominal inspection and pain assessment (bladder, back, pelvis) before, during, and after instillation)
 
Completely drain the bladder prior to instillation of medication for maximum medication concentration in the bladder.
 
Assessments as per the schedule in Section 3.3
 
EORTC-QLQ-NMIBC-24
 
EORTC-QLQ-C30
 
Medication journal
 
Assessment of complementary, alternative, and integrative therapies for the prior 3 months
 
Acupuncture Expectancy and Treatment Preference Questionnaire

2 +/-7	BCG Treatment 2	
Patient will receive BCG instillation #2 with/without acupuncture intervention as per their study arm assignment
 
Review of Medication List
 
Urinanalysis
 
Vital signs to include BP, pulse, temperature
 
Assessment of ability to retain intravesical instillation for the desired dwell time (1-2 hours). Anticholinergic medications may be prescribed per clinic protocol if the patient complains of bladder spasms
 
Brief physical exam: perineal and abdominal inspection and pain assessment (bladder, back, pelvis) before, during, and after instillation)
 
Completely drain the bladder prior to instillation of medication for maximum medication concentration in the bladder.
 
Assessments as per the schedule in Section 3.3
 
EORTC-QLQ-NMIBC-24
 
EORTC-QLQ-C30
 
CTCAE v.50 assessment of Systemic Therapy Toxicity assessing symptoms over the prior week
 
Medication journal

3 +/- 7	BCG Treatment 3	
Patient will receive BCG instillation #3 with/without acupuncture intervention as per their study arm assignment
 
Review of Medication List
 
Urinanalysis
 
Vital signs to include BP, pulse, temperature
 
Assessment of ability to retain intravesical instillation for the desired dwell time (1-2 hours). Anticholinergic medications may be prescribed per clinic protocol if the patient complains of bladder spasms
 
Brief physical exam: perineal and abdominal inspection and pain assessment (bladder, back, pelvis) before, during, and after instillation)
 
Completely drain the bladder prior to instillation of medication for maximum medication concentration in the bladder.
 
Assessments as per the schedule in Section 3.3
 
EORTC-QLQ-NMIBC-24
 
EORTC-QLQ-C30
 
CTCAE v.50 assessment of Systemic Therapy Toxicity assessing symptoms over the prior week
 
Medication journal

4 +/- 7	BCG Treatment 4	
Patient will receive BCG instillation #4 with/without acupuncture intervention as per their study arm assignment

		
Review of Medication List
 
Urinanalysis
 
Vital signs to include BP, pulse, temperature
 
Assessment of ability to retain intravesical instillation for the desired dwell time (1-2 hours). Anticholinergic medications may be prescribed per clinic protocol if the patient complains of bladder spasms
 
Brief physical exam: perineal and abdominal inspection and pain assessment (bladder, back, pelvis) before, during, and after instillation)
 
Completely drain the bladder prior to instillation of medication for maximum medication concentration in the bladder.
 
Assessments as per the schedule in Section 3.3
 
EORTC- QLQ-NMIBC-24
 
EORTC-QLQ-C30
 
CTCAE v.50 assessment of Systemic Therapy Toxicity assessing symptoms over the prior week
 
Medication journal

5 +/- 7	BCG Treatment 5	
Patient will receive BCG instillation #5 with/without acupuncture intervention as per their study arm assignment
 
Review of Medication List
 
Urinanalysis
 
Vital signs to include BP, pulse, temperature
 
Assessment of ability to retain intravesical instillation for the desired dwell time (1-2 hours). Anticholinergic medications may be prescribed per clinic protocol if the patient complains of bladder spasms
 
Brief physical exam: perineal and abdominal inspection and pain assessment (bladder, back, pelvis) before, during, and after instillation)
 
Completely drain the bladder prior to instillation of medication for maximum medication concentration in the bladder.
 
Assessments as per the schedule in Section 3.3
 
EORTC- QLQ-NMIBC-24
 
EORTC-QLQ-C30
 
CTCAE v.50 assessment of Systemic Therapy Toxicity assessing symptoms over the prior week
 
Medication journal

6 +/- 7	BCG Treatment 6	
Patient will receive BCG instillation #6 with/without acupuncture intervention as per their study arm assignment
 
Review of Medication List
 
Urinanalysis
 
Vital signs to include BP, pulse, temperature
 
Assessment of ability to retain intravesical instillation for the desired dwell time (1-2 hours). Anticholinergic medications may be prescribed per clinic protocol if the patient complains of bladder spasms
 
Brief physical exam: perineal and abdominal inspection and pain assessment (bladder, back, pelvis) before, during, and after instillation)
 
Completely drain the bladder prior to instillation of medication for maximum medication concentration in the bladder.
 
Assessments as per the schedule in Section 3.3
 
EORTC- QLQ-NMIBC-24
 
EORTC-QLQ-C30
 
CTCAE v.50 assessment of Systemic Therapy Toxicity assessing symptoms over the prior week
 
Medication journal

7 +/- 14	Follow-up	Review of Medication List

	
Vital signs to include BP, pulse, temperature
 
Physical exam
 
Performance Status
 
EORTC-QLQ-NMIBC-24
 
EORTC-QLQ-C30
 
CTCAE v.50 assessment of Systemic Therapy Toxicity assessing symptoms over the prior week
 
Medication journal
 
Follow-up assessment of complementary, alternative, and integrative therapies
 
Exit Questionnaire

--	---

## 9.0 SUBJECT DISCONTINUATION OF ACTIVE TREATMENT

Subjects may be removed from this study at any time at their discretion. Subjects may also be removed from this protocol if they develop any untoward side effects from the study treatment (acupuncture).

If a subject withdraws consent to participate in the study or aspects of the study, we will request permission to record survival data up to the protocol-described end of the subject follow-up period.. Documentation in the medical record should state that the subject is withdrawing from the study and what, if any, selected data the subject will permit the investigator to obtain.

If a subject withdraws from the study, they will not be replaced. Patients who withdraw or whom are removed from the study by their primary urologist (e.g. in whom their primary urologist determines it is not safe or indicated to proceed with BCG induction due to side effects, other comorbidities, lack of tolerance, or other patient-related concerns) will be surveyed to determine the reason for withdrawal. I.e. An explanation for discontinuing treatment is recorded for each subject discontinuing treatment on the appropriate CRF/eCRF. All subjects, irrespective of treatment status, will continue to be followed for survival. Treatment in this study must be discontinued for any of the following reasons:

- if the Sponsor decides to stop the study;
- at Investigator's discretion;
- at the subject's request;
- if the subject enrolls in a trial of another investigational agent;
- Grade 4 or life-threatening toxicity (See Section 11, Adverse Events) attributable to acupuncture;
- toxicity reactions of Grade 3 or higher, according to the grading in Appendix X - NAME Grading Scale
- pregnancy;
- development of severe BCG toxicity or side effects, e.g. BCG-sepsis, severe refractory BCG cystitis, that preclude the patient from being able to tolerate further BCG instillation.

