#### 3.1.2 Secondary Objectives

To test whether acupuncture may help patients complete the 6-weekly instillations of intravesical BCG. This will be assessed through a patient's completion of BCG regimen, patient-reported outcomes of urinary symptoms and overall quality of life (as measured by the EORTC QLQ-NMIBC-24(1) and EORTC QLQ-C30(2) scales, respectively) and quantification of medication use for symptom management.

To achieve this objective, we will:

1. Compare rates of BCG treatment adherence between arms, as measured by treatment completion, treatment interruptions, and tolerance of treatment retention as measured by time retained, and dose reduction.
2. Compare patient-reported outcomes of urinary symptoms and overall quality of life between arms, as measured by the EORTC QLQ-NMIBC-24 and EORTC QLQ-C30 scales, respectively.

Quantify and compare use of medications for symptom management in patients in the intervention and waitlist control arms, as measured by medication use questionnaire.

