#### **14.6 Indications for Stopping**

Patients participation will be terminated for the following indications:

- If they express a preference to no longer part in the study/personal preference.
- For major side effects or toxicities or complications associated with acupuncture resulting in patient request to not continue
- If the study investigators determine that it is no longer safe or feasible for a patient to continue to receive BCG or acupuncture due to progression of bladder cancer or other comorbid conditions.

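### Section 9.0 seeks survival data, which no endpoint uses, after withdrawal and does not name the BCG outcomes, while 9.0 and 14.6 do not separate stopping acupuncture from ending data collection

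*Combined protocol and SAP*

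**What the plan says.** Section 3.1.2 gives the secondary objective: "To test whether acupuncture may help patients complete the 6-weekly instillations of intravesical BCG". Section 14.2.2 item 1 measures it by instillations given out of six, interruptions, weeks missed, dwell time and dose reductions, compared between arms.

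Section 9.0 covers withdrawal of consent to the study or to parts of it. The only data it names in the request are survival data: "we will request permission to record survival data up to the protocol-described end of the subject follow-up period". It adds that the medical record should state "what, if any, selected data the subject will permit the investigator to obtain". It goes on: "All subjects, irrespective of treatment status, will continue to be followed for survival". It also says "If a subject withdraws from the study, they will not be replaced".

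On leaving because of acupuncture, Section 9.0 says "Subjects may also be removed from this protocol if they develop any untoward side effects from the study treatment (acupuncture"). Section 14.6 begins "Patients participation will be terminated for the following indications". Its list includes "For major side effects or toxicities or complications associated with acupuncture resulting in patient request to not continue", and a decision by the investigators that either BCG or acupuncture can no longer be given safely or feasibly because of progression or comorbidity.

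Section 7.7 plans an end-of-treatment (EOT) visit for everyone who discontinues from the study, 7 to 30 days after the last intravesical dose. It covers adverse events, both EORTC questionnaires, and medication and complementary-therapy lists. No item records BCG delivery.

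**The concern.** The rule for data after withdrawal names a variable that the trial does not analyse and leaves out the one that answers its secondary objective. BCG delivery is standard care, given weekly in the study clinic. For most patients it can be read from the record without a further visit or questionnaire.

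A patient can stop acupuncture and continue BCG. If stopping acupuncture ends participation, and nothing provides for recording BCG delivery afterwards, the outcome may be missing although the clinic holds it. An exit triggered by acupuncture side effects exists only in Arm A, and the reason for leaving may be related to how well the patient tolerates treatment generally. A comparison restricted to patients with data would then no longer be the randomised one. The protocol says these results are to inform power calculations for a Phase III trial, so a distorted completion rate would carry forward.

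**Working it through.** **1. Is survival used anywhere?** The synopsis endpoints, 14.2.1 and 14.2.2 contain no survival endpoint. The visit table in 8.1 and the calendar in Appendix D contain no survival assessment. Participation lasts eight weeks according to the synopsis.

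**2. Is BCG delivery provided for after withdrawal?**

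| Item | Analysed in 14.2.2 | Named in the 9.0 request | In the 7.7 EOT list |
|---|---|---|---|
| Survival | no | yes | no |
| Instillations given, delays, dose reductions | yes | no | no |
| Dwell time | yes | no | no |
| EORTC questionnaires | yes | no | yes |
| Medication | yes (pill counts) | no | yes (list) |

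The EOT visit is timed from the last intravesical dose, so scheduling it needs a BCG date that 9.0 does not ask to record.

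**3. Does the plan say who is analysed?** Section 14 states no analysis set and no handling of missing outcomes.

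**4. The plan's own figure.** Section 14.3 gives a detectable difference of 0.4 for binary endpoints at 80% power and 5% significance (taken here as two-sided). With 45 patients randomised 2:1, the arms are 30 and 15. The normal approximation is

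power = Φ[(d − 1.96·SE0)/SE1], with SE0 = √{p̄(1−p̄)(1/15 + 1/30)} and SE1 = √{pB(1−pB)/15 + pA(1−pA)/30}.

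No control rate is stated, so a range is needed. For 0.4 against 0.8: p̄ = (15×0.4 + 30×0.8)/45 = 0.667, SE0 = 0.149, SE1 = 0.146, and power = Φ(0.738) = 0.77. For 0.5 against 0.9, power is 0.84. The difference detectable with 80% power is 0.40, 0.42, 0.43, 0.41, 0.39 and 0.35 for control rates 0.1, 0.2, 0.3, 0.4, 0.5 and 0.6. The stated 0.4 is therefore reproduced to its one decimal, and this point does not dispute it.

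**5. What missing Arm A outcomes would do.** The plan gives no dropout rate. Assume that k of the 30 Arm A outcomes are missing and that true completion is 18/30 = 0.60. The observed rate lies between (18−k)/(30−k), if all the missing patients completed, and 18/(30−k), if none did. The best-to-worst-case width for the randomised arm is k/30.

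| k (assumed) | Observed rate, range | Width k/30 | Power, 0.4 vs 0.8 | Power, 0.5 vs 0.9 |
|---|---|---|---|---|
| 0 | 0.60 | 0 | 0.77 | 0.84 |
| 3 | 15/27 = 0.56 to 18/27 = 0.67 | 0.10 | 0.75 | 0.82 |
| 6 | 12/24 = 0.50 to 18/24 = 0.75 | 0.20 | 0.73 | 0.80 |

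The power loss is about 2 to 4 points. The observed rate can move by up to 0.75 − 0.60 = 0.15.

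These are extremes for completion as yes/no. For the number of instillations, a patient who leaves after j of six has a value between j and 6. The mean is then uncertain by at most k(6−j)/30 instillations when all k leave at the same point, so early instillations already narrow the gap.

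**The case against.** The strongest reply is that the plan already allows for more than survival. Section 9.0 contemplates withdrawal from only part of the study and has the record state which data the patient permits. It also records the reason for discontinuing treatment. Section 7.7 collects adverse events, questionnaires and medication from those who discontinue. This stands: it would be wrong to say that survival is all that can be collected. It does not fill the gap, because neither section names BCG delivery.

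A reader might infer that every acupuncture-only stop ends participation. The documents do not support that. Removal for side effects in 9.0 is permissive, the toxicity item in 14.6 also needs the patient's request, and its preference item concerns leaving the study in either arm. Section 9.0 also lists reasons for discontinuing treatment, with follow-up continuing irrespective of treatment status, so the two are partly separated, though only for survival.

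A reader might also infer that the BCG outcomes are lost. No section says that they are discarded or unobtainable; they are not provided for. Where the urologist ends BCG, non-completion is already known. The consent form is not in the documents reviewed, so whether it already authorises record access after withdrawal cannot be judged.

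Nor do the documents support the idea that controls will leave out of disappointment. They receive four acupuncture coupons after study completion, which is a reason to stay. Section 3.3.2 does predict better retention in the acupuncture arm, so the sponsor itself expects unequal retention, but the net direction cannot be settled from the text.

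Finally, retention and reasons for leaving are primary outcomes of a feasibility trial, so unequal loss will be reported. That makes the loss visible but does not recover the BCG data.

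**Conclusion.** The point holds as a cheap improvement that should be made. Section 9.0 asks for a variable with no use in this trial and does not name the BCG outcomes. Sections 9.0 and 14.6 do not say that data collection continues when only acupuncture stops. With exits specific to Arm A, no replacement and no stated analysis set, BCG outcomes may be missing differently by arm.

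The size is unknown. The 0.10 and 0.20 widths rest on an assumed 3 or 6 missing Arm A outcomes, and the observed-rate ranges rest also on an assumed true rate of 0.60. They show what such losses could do, not what is expected. The concern is bias rather than power, and it touches secondary outcomes only.

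**What to change.** - **Section 9.0, request at withdrawal.** Replace the request for survival data with a request for permission to record from the medical record the number, dates and strength of BCG instillations, delays, and the reason for stopping, through the end of the patient's induction course. Replace the follow-up-for-survival sentence in the same terms.
- **Sections 9.0 and 14.6.** State that stopping acupuncture alone does not end collection of BCG outcomes. Reconcile both with the EOT visit in 7.7, which already covers adverse events, questionnaires and medications. This concerns data collection only; it does not alter when any treatment is stopped.
- **Section 14.2.2 item 1.** Analyse the chart-derived parts (instillations, interruptions, weeks missed, dose reductions) in all randomised patients by assigned arm. Dwell time depends on the patient reporting the time of first void to the coordinator, so the chart cannot be relied on to recover it. Report it as observed, with the number missing by arm.

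The cost is protocol and consent wording and brief chart abstraction for each withdrawn patient. Some patients may refuse, or may receive BCG elsewhere, so some gaps will remain and should be counted by arm.

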Induction BCG procedures. Patients undergoing induction BCG present once weekly to the UWMC Urology Clinic. They are routinely requested to present 1 hour prior to their scheduled intravesical instillation at which time a urinalysis is obtained to rule out gross hematuria or concern for urinary tract infection. They are then brought into the clinic exam room where a foley catheter is placed by a nurse or advanced practice provider. The bladder is emptied completely. Then the BCG solution (50mL) is instilled into the catheter over 1-3 min by gravity. The catheter is removed, and the patient discharged from clinic. Patients are instructed to attempt to maintain the medication in their bladder (avoid voiding) for two hours, at which time they may void the medication normally with appropriate precautions to ensure deactivation of the live attenuated vaccines. This procedure is repeated weekly for six weeks. If patients report gross blood in the urine or are found to have a urinalysis consistent with urinary tract infection at the time presentation, or are having severe symptoms of cystitis or bladder pain, treatment is deferred for that week in consultation with their treating physician.

Arm A: Acupuncture intervention. After providing a urinary sample for a screening urinalysis prior to BCG treatment, patients randomized to the acupuncture intervention will be escorted to a consultation room where they will meet with the study acupuncturist. Over the next 45-60 minutes the following protocol will be implemented:

Position. The patient will lay in a comfortable position on a portable acupuncture table. Specifically, the patient will lay in the lateral recumbent position on their preferred side.

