Symptom management. All patients will receive standard of care medications to treat symptoms (e.g. anticholinergics such as oxybutynin, tolterodine, darifenacin, solifenacin, trospium, fesoterodine; Beta-3 adrenergic agonists such as mirabegron, local analgesics such as phenazopyridine, narcotic medications such as oxycodone if necessary, nonnarcotic medications such as Tylenol and non-steroidal anti-inflammatory medications) as indicated.

Arm B: Waitlist control arm. To minimize differences in experience between the acupuncture intervention and waitlist control arms, patients in the waitlist control arm will be escorted to the same Consultation room where the acupuncture is performed and asked to lie in a comfortable position (similar to Arm A) prior to their intravesical therapy for an identical period of time before being moved to a treatment room for intravesical instillation of BCG, according to the standard protocol detailed above. At the conclusion of the trial participants in the waitlist control arm will receive coupons to receive 4 free acupuncture appointments. All patients will receive standard of care to treat symptoms (e.g. narcotic and nonnarcotic medications, local analgesics, anticholinergic medications) as indicated.

Follow-up data collection. On a weekly basis, prior to BCG instillation and adjunctive acupuncture therapy (if applicable), patients in both the intervention and waitlist control arms will be assessed using the following metrics:

Week 1	EORTC-QLQ-NMIBC-24 EORTC-QLQ-C30 Medication Journal Assessment of complementary, alternative, and integrative therapies Acupuncture expectancy and treatment preference
Week 2	EORTC-QLQ-NMIBC-24 EORTC-QLQ-C30 CTCAE v.50 assessment of Systemic Therapy Toxicity assessing symptoms over the prior week Medication Journal
Week 3	EORTC-QLQ-NMIBC-24 EORTC-QLQ-C30 CTCAE v.50 assessment of Systemic Therapy Toxicity assessing symptoms over the prior week Medication Journal
Week 4	EORTC-QLQ-NMIBC-24 EORTC-QLQ-C30 CTCAE v.50 assessment of Systemic Therapy Toxicity assessing symptoms over the prior week Medication Journal
Week 5	EORTC-QLQ-NMIBC-24 EORTC-QLQ-C30 CTCAE v.50 assessment of Systemic Therapy Toxicity assessing symptoms over the prior week Medication Journal
Week 6	EORTC-QLQ-NMIBC-244 EORTC-QLQ-C30 CTCAE v.50 assessment of Systemic Therapy Toxicity assessing symptoms over the prior week Medication Journal
Week 7	EORTC-QLQ-NMIBC-24

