#### 7.4 Duration of Therapy

Therapy is administered weekly for a total of 6 weeks. If a patient's therapy is deferred for one week due to infection, gross hematuria, symptoms, or other reasons (e.g. travel, personal reasons why a patient may not attend a scheduled clinic visit, travel issues), patients will resume therapy the next week they are able to do so.

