#### 7.6 Dosing Delays/Dose Modifications

- A urine analysis will be performed prior to instillation. If bactiuria is present on high power field or >5 WBCs are present on high power field and/or gross hematuria is noted and/or the patient complains of acute cystitis symptoms (urinary urgency, frequency, dysuria), instillation is deferred and urine is sent for culture to confirm the presence of UTI and sensitivity to culture. Appropriate antibiotic therapy is prescribed per standard of care clinical practice. Findings are discussed with the prescribing clinician. Microscopic hematuria only or isolated WBCs in an otherwise asymptomatic patient do not preclude treatment.
- For patients reporting severe bladder pain, bladder spasms, urgency/frequency, in consultation with their primary urologist, the dose of BCG may be decreased to half-strength (25mg/50mL) as indicated.

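### Section 9's leftover Grade 3 bullet, if applied as written, would end acupuncture in Arm A patients with Grade 3 BCG symptoms who can continue BCG

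*Combined protocol and SAP*

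**What the plan says.** Section 9 makes discontinuation compulsory for each item in its list. Three items concern toxicity:

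- the item at issue here: "toxicity reactions of Grade 3 or higher, according to the grading in Appendix X - NAME Grading Scale";
- the item listed just before it, which does name a cause: "Grade 4 or life-threatening toxicity (See Section 11, Adverse Events) attributable to acupuncture";
- the last item, which covers severe BCG effects only if they are such "that preclude the patient from being able to tolerate further BCG instillation".

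The opening paragraph of Section 9 identifies the study treatment as acupuncture. Section 11.5 grades all adverse events by CTCAE v5.0. Section 17 lists Appendices A to D, none of which is a toxicity scale.

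Elsewhere the protocol plans for severe BCG symptoms without ending treatment. Under Section 3.3, if patients have gross hematuria, signs of urinary infection, "or are having severe symptoms of cystitis or bladder pain, treatment is deferred for that week in consultation with their treating physician". Under Section 7.4, after a deferral "patients will resume therapy the next week they are able to do so". Under Section 7.6, for severe pain, spasm or urgency and frequency, "the dose of BCG may be decreased to half-strength (25mg/50mL) as indicated".

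Section 3.3 also sets the timing of assessments: each week, "prior to BCG instillation and adjunctive acupuncture therapy (if applicable), patients in both the intervention and waitlist control arms will be assessed". From week 2 these include CTCAE toxicity over the previous week.

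Section 14.2.1 counts an Arm A patient as adherent only if the acupuncture sessions and the follow-up surveys are completed. Arm B needs the surveys only. The denominator is everyone enrolled, and the reasons for departures are reported.

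**The concern.** The Grade 3 bullet does not say what must have caused the toxicity, although the bullet before it does. BCG commonly causes urinary and pelvic symptoms, and Section 3.3.2 expects them to grow with each dose. A patient with Grade 3 BCG cystitis who recovers enough to resume BCG would, on the words of the bullet, have to give up acupuncture. The intervention would be taken away from the kind of patient it is meant to help, probably in the later weeks.

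Two things are at stake. Clinic staff would have contradictory instructions for that patient. And one primary feasibility measure, adherence in Arm A, would be lowered by the protocol's own rule rather than by patients declining acupuncture. That measure is meant to inform the Phase III design.

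**Working it through.** **Step 1. One patient, each rule.** Take an Arm A patient with Grade 3 bladder pain after dose 3. BCG is deferred for a week and can then be resumed, at full or half strength.

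| Section | What it implies for this patient |
|---|---|
| 3.3, 7.4, 7.6 | Defer, resume when able, reduce the dose if needed |
| 9, Grade 4 bullet | Not triggered: not Grade 4, not due to acupuncture |
| 9, BCG-intolerance bullet | Not triggered: further BCG is tolerable |
| 14.6 | Not triggered: its toxicity item covers acupuncture-related events that lead the patient to ask to stop; its safety item concerns cancer progression or other comorbidity |
| 9, Grade 3 bullet, graded by CTCAE v5.0 | Triggered: treatment must stop |

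Only the Grade 3 bullet ends acupuncture here. To reach that result the reader must supply CTCAE from Section 11.5, because the scale the bullet names does not exist.

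**Step 2. Cost of one forced stop.** Section 14.3 gives 45 patients at 2:1, so Arm A has 45 × 2/3 = 30. A patient who would otherwise have adhered and is stopped before session 6 fails the Section 14.2.1 definition. The loss is 1/30 = 3.3 percentage points in Arm A, or 1/45 = 2.2 points if the two arms are pooled. Arm B cannot lose adherence this way.

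**Step 3. How many stops?** The documents do not say. The following is an illustration, and every input except n = 30 is assumed:

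- r, the share of Arm A with any Grade 3 or higher BCG event: 5%, 20% or 40%. The 40% borrows the BCG-interruption figure in Section 2.1, which is not a Grade 3 rate.
- Half of these patients would stop anyway for BCG intolerance.
- An event after dose 6 costs no session. With even onset over the six doses, the chance that the event falls early enough to matter is 5/6 = 0.833. With onset weighted 1 to 6 (sum 21), it is 15/21 = 0.714.

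Forced stops due to the bullet = 30 × r × P(early enough) × 0.5.

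| r | Even onset: stops (points lost) | Rising onset: stops (points lost) |
|---|---|---|
| 5% | 0.6 (2.1) | 0.5 (1.8) |
| 20% | 2.5 (8.3) | 2.1 (7.1) |
| 40% | 5.0 (16.7) | 4.3 (14.3) |

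The result runs from less than one patient to about five, depending on the assumptions. Once the bullet is removed or limited to acupuncture toxicity, BCG symptoms force no stops under it.

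**The case against.** The best defence is that nobody would apply this bullet. Its scale is a placeholder, and similar residue stands elsewhere: drafting instructions in Section 7.0, template headings in Section 5.2, unfilled day windows in Appendix D. Section 14.6 and the opening of Section 9 both tie toxicity-related removal to acupuncture, so a sensible reader would do the same here. This largely stands. The text is ambiguous, and the harm depends on someone importing CTCAE and following the words. But the bullet sits in a compulsory list, nothing tells staff to ignore it, and Section 11.5 supplies an obvious scale.

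The second defence is that the effect on reporting is limited. Adherence is descriptive, with no test or threshold, and reasons for stopping are recorded under Sections 9 and 14.2.1. Patients who stop BCG for intolerance miss acupuncture sessions in any case, so the proportion already reflects BCG tolerance. This also stands, but traceability does not restore sessions that were withheld.

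Several stronger readings are tempting but unsupported:

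- **That the trigger would be met routinely.** Section 3.3 shows that toxicity is assessed weekly, not that Grade 3 is reached often.
- **That the severe-event figure of nearly 70% in Section 2.1 predicts the stops.** No grading scale is given for it.
- **That up to 10 of 30 would be lost.** That is 30 × 0.40 × 5/6, and it includes patients whom BCG intolerance would stop anyway.
- **That the any-cause reading must be right because it makes the Grade 4 bullet redundant.** A Grade 3 rule limited to acupuncture would make it redundant too. The any-cause reading also leaves little work for the BCG-intolerance bullet, which counts against it.
- **That the bullet would also stop BCG and so contradict Section 4.1.** This needs the less natural meaning of treatment, given that Section 9 identifies it as acupuncture.

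**Conclusion.** The point holds in a limited form. Section 9 contains an evident template remnant with no attribution and no usable scale. Applied as written with CTCAE v5.0, it would end acupuncture in Arm A patients with Grade 3 BCG symptoms who can continue BCG. That runs against how the rest of the protocol handles such patients, and it would lower a primary feasibility measure in one arm only. It is a wrong instruction rather than a missing detail, so it deserves correction even though staff may well disregard it.

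The size is unknown. What can be stated is 3.3 percentage points of Arm A adherence for each forced stop, assuming 30 patients in the arm and that the patient would otherwise have adhered. The illustrative counts rest on assumed rates, onset patterns and BCG-intolerance shares, and should not be read as predictions.

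**What to change.** Leave the Grade 4 bullet and the BCG-intolerance bullet in Section 9 unchanged. For the placeholder bullet, do one of two things:

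1. Delete it; or
2. Reword it: *Grade 3 toxicity (CTCAE v5.0) that the investigator attributes to acupuncture rather than to BCG: discontinue acupuncture; BCG continues or is modified per Sections 4.1 and 7.6; study assessments continue.*

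The investigators choose between these by deciding whether Grade 3 acupuncture toxicity should force a stop. Less clear cases remain with the existing investigator-discretion item.

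The toxicity bullets should not be merged into one that requires a definite or probable relation. Section 11.6 counts possibly related events as related, so a merged rule could remove the compulsory stop for a Grade 4 event possibly due to acupuncture. Conversely, using the full Section 11.6 definition at Grade 3 could bring BCG cystitis back in as possibly related, because acupuncture is given just before BCG. Hence the wording that asks the investigator to choose between the two causes.

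The cost is a short wording amendment, with no extra data, visits or patients. Section 14.2.1 already asks for reasons and needs no change.
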